6.2.1 Screening/Recruitment appointment

The screening appointment will be held on-site or remotely during a routine clinic visit. This will be followed up by the remote Recruitment appointment where informed e-consent will be obtained before any trialspecific procedures take place. Reviewing eligibility based on clinician diagnosis or medical history will be done prior to consent.

6.2.1.1 Informed consent

A participant or parent/carer should give their written informed consent or e-consent to take part in the study before any trial-specific procedures are conducted. A young person who has sufficient understanding and intelligence to understand fully what is proposed and can use and weigh this information in reaching a decision (i.e. they are 'Gillick competent'), can give consent to treatment. For children or young people not competent, parents (and those with parental responsibility) can consent to medical treatment on their behalf. Consent of only one parent/carer is required. The consent will be taken by the Research Nurse, who has been trained on Good Clinical Practice (GCP) and the study protocol. Before providing consent, the participant and/or parent/carer should have the opportunity to ask any questions they might have. The signed and dated consent form should be printed out and filed in the investigator site file and a copy provided to the participant. Consent must also be documented in the participant's medical notes, in accordance with GCP.

Participants are free to withdraw from the study at any time without giving a reason, without this affecting the treatment they receive.

6.2.1.2 Eligibility screening

The participants' eligibility will be determined against all criteria. In addition, if a patient is of childbearing potential, a pregnancy test should be conducted at Baseline appointment if a patient is confirmed to be eligible. Any criteria related to medical tests, history or medication use must be confirmed against the participant's medical notes before the patient is randomised at Baseline appointment. The research team should therefore request for the relevant sections of the participant's medical records, including from the patient's GP, if not included in the referral information, prior to the Baseline appointment unless the participant has themselves requested for the information.

During the Screening/Recruitment appointment, the patient should be evaluated against the following study entry criteria:

Age

Participants must be aged 3-18 years

FAPD

Participants must meet the Rome IV criteria for FAPD (Group H2) [23] (see **4.1 INCLUSION CRITERIA**). FAPD must be either a confirmed existing diagnosis based on Rome IV criteria and recorded in the participant's medical records, or a diagnosis confirmed by the PI or a delegated member of staff. The FAPD (Group H2) sub-type will be recorded.

Faecal calprotectin level

Participants must have a normal faecal calprotectin at diagnosis of their FAPD (<250ug/g stool age 3-8 yrs, <100ug/g stool age 9-18 yrs).

Exclusion of other conditions

Participants should not be enrolled into the study until any required tests to exclude other conditions have been performed.

Confirming eligibility and suitability based on medical records

The patient's medical history and medications should be reviewed to confirm the patient's eligibility and suitability to take part in the trial. If any testing was required to exclude other intestinal conditions, the results from these tests must be obtained before the patient can proceed in the study.

Any patients failing at one or more of the assessments above, should not proceed in the trial and will return to standard-of-care.

Medical history and concomitant medications

Patients using probiotic supplements, other intestinal adsorbents (activated charcoal, kaoline, diosmectite), slow-release medications or strong opioids (World Health Organisation Step III) are not eligible to take part in the study. A list of concomitant medications from hospital records should be assessed and eligibility confirmed at Baseline appointment. Patients using antidepressant agents are not eligible unless these were used at a stable dose for at least 6 weeks

Pregnancy test for women of childbearing potential

A negative pregnancy test must be obtained from any female participants of childbearing potential at the

Baseline appointment, this will be completed at home on the day of the appointment and confirmed with the investigator.

4.2.1.3. Demographic information

Age, sex and ethnicity should be recorded in the eCRF.

6.2.1.4 Adverse Events (AEs)

Any AEs related to the conduct of the study procedures should be recorded.

6.2.1.5 Randomisation

At Baseline appointment eligible participants will be randomised to blinded treatment by the Research Nurse at each site, who has access to the randomisation tool. The randomisation tool is built into a secure, restricted access web-based eCRF system developed and hosted by Sealed Envelope Ltd. The system will only allow participants to be randomised if they are confirmed to meet all the eligibility criteria listed on the randomisation eCRF.

The randomisation tool will provide a unique randomisation code, which the site research team will record on a treatment request form and email to the Sponsor's unblinded study supplies coordinator. The coordinator will check the code against the randomisation code list to obtain the treatment group allocation and will then schedule a courier shipment of the corresponding treatment to the participant's home address.

At Baseline appointment the Research Nurse will inform the participant if they are eligible to continue in the study or return to standard of care.

6.2.1.6 Treatment instructions

At Recruitment and baseline appointments the Research Nurse will instruct the participant and/or parent/carer on how to use the age-appropriate blinded study treatment during the double-blind phase. Each patient will receive a copy of the written study treatment use instructions (APPENDIX C: TREATMENT USE INSTRUCTIONS (DOUBLE-BLIND PHASE).

6.2.1.7 Diary and questionnaires

At Recruitment appointment the Research Nurse will explain the study diary and questionnaires (PedsQL-3.0-GIS and KIDSCREEN-27).

Participants will be enrolled into the study and/or parents/carers will be sent a text and email with a link to the online questionnaires (PedsQL-3.0-GIS and KIDSCREEN-27) to be completed at Recruitment visit. For the duration of the study, each evening at 6 pm a text and email will be sent with a link to that day's diary and questionnaires (recruitment, end of double-blind and open label phases). Participants and/or parents will also be able to complete the previous day's diary if uncompleted.

The content of the diary/questionnaires is provided in Error! Reference source not found...

6.2.2 Follow-up appointments

The participants will attend follow-up remote appointments by video or telephone call at week 6 (end of blinded treatment period) and week 10 (end of open-label treatment period). The date and time of the

appointment will be agreed by telephone or email, with email confirmation and attached instructions on accessing the video consultation or call. At both follow-up remote appointments, the following should be conducted:

- Completion of questionnaires (PedsQL-3.0-GIS and KIDSCREEN-27)
- Review of AEs
- Review of any changes in medical history or medications
- Adequate relief question

Additional, visit-specific procedures are described below.

6.2.2.1 Week 6

In addition to the completion of questionnaires and review of AEs and changes in medical history or medications, the following should be conducted:

I. All participants will receive instructions on how to take Enterosgel® for the open-label phase (Error! Reference source not found..

6.2.2.2 Week 10

In addition to the completion of questionnaires and review of AEs and changes in medical history or medications, the following should be conducted:

- I. The participants will be explained that they will no longer receive any study treatments and are returning to standard of care.
- II. For participants who want to continue to use Enterosgel, they will be advised regarding its availability as an OTC product or through a prescription from their General Practitioner

6.2.3 Unscheduled visits

Any unscheduled clinic visits, hospitalisations or visits to the Accident & Emergency department due to FAPD or due to AEs potentially related to study treatment, should be recorded in both medical records and the relevant eCRF.

6.3 DESCRIPTION OF ASSESSMENTS

6.3.1 Study diary

Data on FAPD symptoms, nursery/school attendance and treatment use will be collected using a studyspecific diary, which is available as an electronic diary that can be completed online by following a link provided on daily email and text message notifications. Questions included in the diary are provided in Error! Reference source not found.. No patient identifiable data will be collected using the electronic diary.

6.3.2 PedsQL-3.0-GIS

The Pediatric Quality of Life Inventory[™] (PedsQL[™]) Gastrointestinal Symptoms Module for patients is a questionnaire for patients with functional gastrointestinal disorders (FGIDs) and organic GI diseases, hereafter referred to as "GI disorders". The module consists of a patient self-report ages 5-18 and parent proxy-report for ages 2-18 years. PedsQL-3.0-GIS evaluates the intensity of symptoms during the previous one month period [2]. The modules are separated into age categories; teens (13-18yrs), child (8-12 yrs), young child (5-7yrs) and toddlers (2-4 years). It considers fourteen unidimensional scales measuring

ENT08UK Clinical Investigation Plan v1_07/05/2025

stomach pain, stomach discomfort when eating, food and drink limits, trouble swallowing, heartburn and reflux, nausea and vomiting, gas and bloating, constipation, blood, diarrhea, worry, medicines, and communication. The "worry about bowel movements" (5 questions) will be compared to study treatment effects on the intervention on anxiety/depression. Each question is scored on a scale from 0 to 4, and their sum is then calculated to obtain the total score. Higher scores indicate worse symptoms. Data suggests that the PedsQL-3.0-GIS has good measurement properties and can be used as a common metrics to compare GI-specific symptoms in clinical research and practice both within and across patient groups for FGIDs [27].

A copy of PedsQL-3.0-GIS is provided in Error! Reference source not found..

6.3.3 KIDSCREEN-27

The KIDSCREEN-27 questionnaires can be used to assess the subjective health and the psychological, mental and social well-being of children and adolescents (HRQoL) between the ages of 8 and 18. The questionnaires can be completed by both healthy and ill children and adolescents themselves as a self-assessment or a corresponding parent version is available for parents for by proxy assessment for age 7 years and below. The questionnaires can be used in hospitals, other medical settings and have been validated in 13 European countries, which allows meaningful cross-cultural comparisons of health-related quality of life. The KIDSCREEN -27 allows a detailed profile of the ten HRQoL dimensions and takes ca. 10 minutes to complete [28]

The questionnaires will be child-self report for participants aged 8-18yrs and parents proxy report for age 3-7yrs. The "General Mood and Feelings about Yourself" sub-score (based on 7 questions) will be compared according to study treatment to assess effects of the intervention on anxiety/depression. A copy of KIDSCREEN-27 is provided in Error! Reference source not found..

6.4 EMERGENCY UNBLINDING

Unblinding (code-break) should only be performed during the trial in a situation where information about the patient's trial treatment is necessary in order to provide the patient with appropriate and optimal medical care. Such emergency unblinding may be requested on the grounds of safety by the Chief Investigator, local PI or authorised delegate or treating physician. A request for unblinding can also come from a patient, carer or GP, for example when an adverse event occurs or there are changes planned to the patient's regular therapy. Requests for unblinding will first be reviewed by the PI or sub-PI who evaluates the information and the importance of unblinding in the given circumstances. If the PI/sub-PI decides that unblinding is necessary to ensure the patient will receive appropriate medical care, emergency unblinding is performed. Unblinding request can be submitted by any local research team member with access to the emailed or sent by a text message or fax to the person who had requested unblinding. Following unblinding, a notification will be automatically sent to the trial manager.

In case of emergency unblinding, the PI will be responsible for deciding whether the patient should continue on trial treatment. Unblinded patients should be followed up according to the study protocol until the end of the study. The reason for emergency unblinding should be recorded in the Emergency Unblinding eCRF.

7. SAFETY

7.1 DEFINITIONS

Types of AEs associated with medical devices and applicable for this study are defined in accordance with the European Commission guidelines on medical devices [29].

7.1.1 Adverse Event (AE)

Any untoward medical occurrence, unintended disease or injury or any untoward clinical signs (including an abnormal laboratory finding) in subjects, users or other persons whether or not related to the investigational medical device.

NOTE 1: This includes events related to the investigational device or the comparator.

NOTE 2: This includes events related to the procedures involved (any procedure in the clinical investigation plan).

NOTE 3: For users or other persons this is restricted to events related to the investigational medical device.

7.1.2 Adverse Device Effect (ADE)

AE related to the use of an investigational medical device.

NOTE 1: This includes any AE resulting from insufficiencies or inadequacies in the instructions for use, the deployment, the implantation, the installation, the operation, or any malfunction of the investigational medical device.

NOTE 2: This includes any event that is a result of a use error or intentional misuse.

7.1.3 Serious Adverse Device Effect (SADE)

Adverse device effect that has resulted in any of the consequences characteristic of a serious AE.

7.1.4 Serious Adverse Event (SAE)

AE that:

a) led to a death,

- b) led to a serious deterioration in health that either:
 - 1. resulted in a life-threatening illness or injury, or
 - 2. resulted in a permanent impairment of a body structure or a body function, or
 - 3. required in-patient hospitalisation or prolongation of existing hospitalisation, or
 - 4. resulted in medical or surgical intervention to prevent life threatening illness or injury or permanent impairment to a body structure or a body function.

c) led to foetal distress, foetal death or a congenital abnormality or birth defect.

NOTE 1: This includes device deficiencies that might have led to a SAE if a) suitable action had not been taken or b) intervention had not been made or c) if circumstances had been less fortunate. These are handled under the SAE reporting system.

NOTE 2: A planned hospitalisation for pre-existing condition, or a procedure required by the Clinical Investigation Plan, without a serious deterioration in health, is not considered to be a SAE.

7.1.5 Unanticipated Serious Adverse Device Effect (USADE)

Serious adverse device effect which by its nature, incidence, severity or outcome has not been identified in the current version of the risk analysis report or product safety information. NOTE: Anticipated: an effect which by its nature, incidence, severity or outcome has been previously identified in the risk analysis report

7.1.6 Expected Adverse Events and Adverse Events of Special Interest

According to the standard Package Information Leaflet, Enterosgel® can cause constipation and nausea. It is normal for patients with IBS-D to feel constipated when diarrhoea symptoms improve. Constipation should only be considered an AE in this study if all of the following are met:

- a) patient complains about it to the site research team
- b) patient had at least 3 consecutive days without bowel movements
- c) clinical intervention is required (i.e. laxative or other treatment)

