2.2.2 Secondary objectives

The secondary objectives for the **double-blind treatment phase** (weeks 3-6) are:

- 1. To determine the efficacy of Enterosgel® compared with a parallel placebo group in terms of:
 - abdominal pain as recorded in the daily diary
 - change in stomach pain and other gastrointestinal symptoms
- 2. To determine effects of treatment on health-related quality of life
- 3. To evaluate safety of Enterosgel® through reported adverse events potentially related to treatment

The secondary objectives for the open-label treatment phase (weeks 7-10) are:

- 4. In patients who had received placebo as blinded treatment, to compare the study outcome measures (same as for double-blind phase above) over the open-label Enterosgel® treatment period to the preceding placebo treatment period.
- 5. In patients who had received Enterosgel® as the blinded treatment, to test whether the treatment benefits (in terms of study outcome measures; same as for double-blind phase above) can be effectively maintained with Enterosgel®.
- 6. To evaluate safety of Enterosgel® through reported adverse events potentially related to treatment.

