10. Adequate relief	Questionnaire	Opinion of the 1) child and 2) parent/carer whether there has been adequate relief of abdominal pain during the previous 7 days (recorded at end of double-blind and open-label phases)
11. Use of common analgesics for abdominal pain	Questionnaire	 Use of common analgesics (e.g. paracetamol; ibuprofen) for abdominal pain in the last week of the initial observation period (week 2), double blind phase (week 6) and open label phase (week 10)
12. Adverse Events	When reported	 Percentage of patients reporting SAEs and AEs possibly related to treatment Total number of SAEs and AEs reported

*Patients who develop constipation will be advised to stop treatment for a few days as per study treatment instructions. The diary will capture this information which will not be considered as non-compliance.

Data regarding the PedsQL 3.0 GIS module and KIDSCREEN-27 questionnaire will be collected as an online version (for use on mobile devices, laptops and computers). The PedsQL 3.0 GIS module will be a proxy-report completed by the parent/carer for 3-4-year-olds and child self-report from 5-18 years. The KIDSCREEN-27 will be a proxy-report completed by the parent/carer for 3-7 year-olds and child self-report from 8-18 years. The "General Mood and Feelings about Yourself" sub-score (based on 7 questions) will be analysed to assess effects of the intervention on anxiety/depression in addition to the "worry about bowel movements" (5 questions) in the PedsQL 3.0 GIS module. The content of the diary is supplied in Error! Reference source not found..

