4. After appropriate evaluation, the symptoms cannot be fully explained by another medical condition *Criteria fulfilled for at least 2 months prior to diagnosis

Within IBS the following are subtypes:

- Abdominal pain associated with constipation (IBS-C)
- Abdominal pain associated with diarrhoea (IBS-D)
- Abdominal pain associated with constipation and diarrhoea mixed (IBS-M)
- Abdominal pain not otherwise specified (IBS-U)

H2c. Abdominal Migraine. Diagnostic criteria* Must include all of the following occurring at least twice:

- 1. Paroxysmal episodes of intense, acute periumbilical, midline or diffuse abdominal pain lasting 1 hour or more (should be the most severe and distressing symptom)
- 2. Episodes are separated by weeks to months
- 3. The pain is incapacitating and interferes with normal activities
- 4. Stereotypical pattern and symptoms in the individual patient
- 5. The pain is associated with two or more of the following:
 - a) Anorexia
 - b) Nausea
 - c) Vomiting
 - d) Headache
 - e) Photophobia
 - f) Pallor

6. After appropriate evaluation, the symptoms cannot be fully explained by another medical condition *Criteria fulfilled for at least 6 months prior to diagnosis

H2d. **Functional Abdominal Pain** – **Not Otherwise Specified** Diagnostic criteria* Must be fulfilled at least 4 times per month and include all of the following:

- 1. Episodic or continuous abdominal pain that does not occur solely during physiologic events (e.g., eating, menses)
- 2. Insufficient criteria for irritable bowel syndrome, functional dyspepsia, or abdominal migraine
- 3. After appropriate evaluation, the abdominal pain cannot be fully explained by another medical condition

*Criteria fulfilled for at least 2 months prior to diagnosis

^{**} A pregnancy test will be performed at Baseline on all female patients of child-bearing potential. Females of childbearing potential (over the age of 11 years; not surgically sterile (hysterectomy or bilateral oophorectomy), 12 months postmenopausal or otherwise incapable of pregnancy) and heterosexually active must use contraception throughout the screening period and the 8 weeks when they may be receiving study treatment. Acceptable methods of contraception are methods that can achieve a failure rate of less than 1% per year when used consistently and correctly are considered as highly effective birth control methods. Such methods include [23]:

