7.2 RECORDING AND REPORTING OF ADVERSE EVENTS

7.2.1 Investigational procedures and treatment

AEs will be collected throughout the study from screening appointment until week 10. If an AE is reported by the patient, the relationship of the event to the study treatment or procedures should be assessed by the local PI, or a delegated sub-PI or nurse. The following information will be recorded for all AEs:

- Medical term of the AE (SNOMED CT terminology)
- Start date and date of resolution
- Seriousness
- Severity
- Study treatment action
- Outcome
- Relationship with the study treatment
- Expectedness

SADEs, SAEs, and USADEs should always be recorded in the eCRF and reported to the Sponsor using the Sponsor's SAE reporting form. Any SAEs that occur during the screening period that resulted from the administration of any study procedures and are unexpected, should also be reported. The form should be emailed to the Trial Manager ([contact]) within 24 hours of the site team becoming aware of the event. If the site does not receive an acknowledgement of the receipt of the report within 24 hours, they should immediately contact the Trial Manager by telephone.

The Sponsor should immediately inform the CI of any reported SAEs. The CI should review the SAE to confirm causality and expectedness.

The Sponsor should also report all serious adverse events, whether initially considered to be device related to the MHRA (Any SAEs which indicate an imminent risk of death, serious injury or serious illness, and which requires prompt remedial action for other subjects, shall be reported within two calendar days of awareness, any other SAEs shall be reported within seven calendar days). The REC should be notified of any related and unexpected SAEs within 15 days. Reports of related and unexpected SAEs in double-blind trials should be unblinded. Investigators should only receive information on the code-break if it is necessary for the safety of the patient.

SAEs should be followed-up until resolution or a final outcome. All follow-up information should be emailed to the Sponsor as soon as it becomes available. The SAE form and any email correspondence related to the SAE should be filed in the investigator site file and in the electronic Trial Master File.

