PedsQL GI Module 3.0 - (13-18) Not to be reproduced without permission Copyright © 1998 [name]. All rights reserved PedsQL-3.0-GIS-Module-A_AU3.0_eng-USori

0

ENT08UK Clinical Investigation Plan v1_07/05/2025

5. It is hard for me to talk to my parents about my illness

2

1

3

4

APPENDIX C. STUDY TREATMENT INSTRUCTIONS DOUBLE-BLIND PHASE **4 WEEK DOUBLE-BLIND PHASE (WEEKS 3-6)** ENTOPIC Treatment instructions for children aged 7-14 years

IMPORTANT! PLEASE READ BEFORE STARTING THE TREATMENT

Enterosgel[®] is a safe, drug-free treatment with 30 years of safe use without any reports of serious adverse events. There is no risk of overdose. You may contact your research nurse at any time to discuss any questions.

HOW TO STORE THE TREATMENT?

- Do not use if the outer tube is damaged
- Keep out of the reach of children
- Store at room temperature (between +4 to +30 °C) and **not** in the fridge

HOW TO TAKE THE TREATMENT?

• Take the treatment 2 hours before or after taking oral medications and 1 hour before or after meals

Preparing a single dose

- Add 20ml room temperature water into the measuring cup
- Shake the tube well before opening and open immediately before use
- Add **all** the contents of the tube into a glass and add the **20ml** of room temperature water, mix well and drink straight away

HOW MANY TIMES A DAY TO TAKE THE TREATMENT?

Week 1 and 2

Use the tubes in the box labelled "WEEK 1-2: Age 7-14 years, Double blind phase study treatment"

Take One DOSE IN THE MORNING & One DOSE IN THE EVENING for 2 weeks

Week 3 and 4

Use the tubes in the box labelled "WEEK 3-4: Age 7-14 years, Double blind phase study treatment"

Take One DOSE IN THE MORNING & One DOSE IN THE EVENING for 2 weeks

PLEASE NOTE: It is important to know that your child's bowel might start changing its habits, including slowing down and not having any stool for 1-2 days. This is completely normal.

If at any time your child does not have a bowel movement (no stool at all) for 2 days, stop the treatment and increase your child's intake of water. After the next bowel movement, continue with a single dose once a day for a few days then return to two doses per day. APPENDIX D. STUDY TREATMENT INSTRUCTIONS OPEN LABEL PHASE

4 WEEK OPEN-LABEL PHASE (WEEKS 7-10) ENTOPIC Treatment instructions for children aged 7-14 years

IMPORTANT! PLEASE READ BEFORE STARTING THE TREATMENT

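### Section 7.1.6 counts constipation, a labelled device effect, as an AE only when it needs clinical intervention, so reported episodes that resolve on their own are left out of the AE and ADE counts

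*Protocol*

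**What the plan says.** Protocol 7.1.6 states that the package leaflet lists constipation and nausea as possible effects of Enterosgel. It remarks that feeling constipated is normal in IBS-D as diarrhoea improves, and then sets a rule: "Constipation should only be considered an AE in this study if all of the following are met". The three conditions are (a) a complaint to the site team, (b) at least three days in a row without a stool, and (c) a need for clinical intervention, such as a laxative. Nausea has no comparable rule.

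Section 7.1.1 defines an AE as "Any untoward medical occurrence, unintended disease or injury or any untoward clinical signs", whether or not related to the device. Section 7.1.2 defines an ADE as "AE related to the use of an investigational medical device". For each AE, section 7.2.1 requires severity, relationship to treatment, outcome, expectedness and "Study treatment action", among other fields.

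The safety objectives in 2.2.2 are to be met "through reported adverse events potentially related to treatment". Outcome 12 of Table 1 (3.2.2.1) is "Percentage of patients reporting SAEs and AEs possibly related to treatment", plus total numbers of SAEs and AEs.

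The footnote to Table 1 says that children who become constipated will be told to stop treatment for a few days, that the diary records this, and that it does not count as non-compliance. The Appendix C sheet (age 7-14) warns families that bowel habit may change, "including slowing down and not having any stool for 1-2 days. This is completely normal". It tells them to stop dosing and give more water after two stool-free days, then to resume at one dose a day before returning to two. Appendix D gives the same advice for the open-label phase.

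**The concern.** A trial run for CE marking purposes (Trial Summary) should be able to report how often a labelled effect occurs in each arm. Here the case definition for that effect is stricter than the protocol's own AE definition, and the added strictness removes the mild and moderate end. The protocol recognises constipation as a reason to withhold the device, yet the same episode need not reach the safety tables.

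The only reason given concerns IBS-D. The trial also enrols functional dyspepsia, abdominal migraine, functional abdominal pain not otherwise specified and all IBS subtypes, including IBS-C (4.1 and the Rome IV notes after 4.2). For most of these, improving diarrhoea does not explain new constipation.

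The placebo is water (5.1.3). If the leaflet is right that the device causes constipation, the uncounted episodes would fall more on the active arm, and the absolute difference in outcome 12 would come out too small.

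**Working it through.** This is a question of definitions. The protocol gives no constipation rate and no share of episodes meeting the conditions, so there is no stated figure to reproduce.

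**Step 1: the rule as logic.** By 7.1.6, constipation is an AE only if (a) and (b) and (c) all hold. By 7.1.2, every ADE is an AE. Failing any one condition therefore removes an episode from both counts.

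| Reported episode | (a) | (b) | (c) | AE? | ADE possible? |
|---|---|---|---|---|---|
| Dosing paused, resolves on day 3 with water only | yes | no | no | no | no |
| Dosing paused, four stool-free days, resolves with water only | yes | yes | no | no | no |
| Hard stools, laxative given, no three-day gap | yes | no | yes | no | no |
| Four stool-free days, laxative given | yes | yes | yes | yes | yes |

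Under 7.1.1 alone, the first three could all be recorded if untoward for that child. Condition (c) by itself removes every episode that resolves without clinical intervention. Condition (a) removes little, since 7.2.1 already works from events the patient reports.

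**Step 2: what other data hold.** The treatment-phase diary (Appendix A) lets the child give constipation as the reason for taking no dose. The one-drink option carries no reason, so the step-down days in Appendices C and D cannot be identified. The three diary questions cover pain, drinks taken and school; none asks about bowel movements, so (b) depends on recall. The 14-item PedsQL constipation scale is a secondary outcome at baseline, week 6 and week 10 with one-month recall. It measures symptoms and does not assess relationship to treatment. None of these opens an AE record or enters outcome 12.

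**Step 3: should every pause be an AE?** Section 4.2 excludes only children averaging fewer than 3 stools a week. Take an eligible child with exactly 3 a week, on separate days, in a repeating weekly pattern:

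- stool-free days per week = 7 − 3 = 4
- gaps between stools per week = 3
- mean gap = 4 / 3 ≈ 1.33 stool-free days, so at least one gap is 2 days or longer.

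The two-day stop advice can thus be triggered weekly by unchanged habit. A pause alone does not show an untoward event.

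**Step 4: direction, by assumption only.** Suppose each affected child has one episode and a share f of episodes meets all three conditions in both arms. Then recorded difference = f × true difference. Assume a true difference of 10 points, which is 0.10 × 77 = 7.7 children per arm:

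- f = 0.10: 1 point, or 0.10 × 7.7 ≈ 0.8 children
- f = 0.50: 5 points, or 0.50 × 7.7 ≈ 3.9 children.

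The risk ratio is unchanged because f cancels. Neither the 10 points nor the range for f comes from the protocol.

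**The case against.** The rule is a deliberate, pre-specified case definition applied alike in both blinded arms. Where constipation belongs to the enrolled disease, as in IBS-C, a threshold above background is reasonable. Step 3 shows that short stool-free gaps can be normal here, which also makes a three-day criterion defensible as a marker. Nausea lacking a threshold is no inconsistency in itself, since the protocol links only constipation to symptom improvement. The diary and PedsQL scale record much of the burden by arm, and the DMC monitors study data for safety (11.2). All of this stands, and it limits both the severity of the point and the remedy. It does not answer why a reported worsening should have no AE record, severity grade or relationship assessment merely because no laxative was needed. Background disease can be handled by the relationship field and the randomised comparison.

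Four stronger readings are tempting but not supported:

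- **That stopping at day 2 means episodes usually fail (b).** Stopping the doses does not end the episode, and (b) can still be met afterwards. The protocol says nothing about how long episodes last.
- **That a SAP could do nothing.** It could tabulate the diary constipation code by arm and phase. It could not recreate AE records or relationship assessments that sites never made.
- **That every treatment pause should be an AE.** Given the eligibility rule on stool frequency, this would turn ordinary habit into AEs.
- **That the rule covers home measures because (c) mentions other treatment.** Stopping doses and drinking water is hardly clinical intervention, and (a) and (b) would still be required.

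**Conclusion.** The point holds and should be fixed. As written, 7.1.6 is narrower than 7.1.1 for a labelled effect, and its IBS-D rationale does not cover the enrolled population. Reported constipation that resolves without clinical intervention, even if it interrupts dosing, is absent from the AE and ADE counts behind the safety objective and outcome 12. This follows from the wording alone.

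The size of the under-count cannot be derived from the document. That it would fall more on the active arm assumes the leaflet is right that the device causes constipation. The episodes concerned are mostly non-serious, and dose-free days and symptoms remain partly visible elsewhere. The primary endpoint is unaffected, and the compliance footnote and per-protocol definition need no change on this account.

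**What to change.** Amend 7.1.6 so that constipation which the child or carer reports as new, or as worse than in the observation phase, is recorded as an AE under 7.1.1 with all the fields in 7.2.1. Keep conditions (b) and (c) only as a flag identifying constipation requiring intervention. State that a precautionary two-day pause without reported worsening need not be an AE.

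Beside the AE table, report the number of children and of days with constipation given as the diary reason for taking no dose, by arm and phase. These data are already being collected.

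The cost is a wording change in 7.1.6, one flag on the AE form and one extra table. Sites will enter a modest number of additional non-serious AEs. Some will be background disease, which the relationship field and the comparison between arms can separate. The wording should change before sites apply the present rule, because AE details not captured at the time cannot be recovered at analysis.
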